8.5.5 Suicidality Monitoring

Suicidality monitoring will occur only in subjects enrolled in Part 2 and at the time points described in the SoA ([Table 1.3-2](#)).

Carbamazepine is known to increase the risk for suicidal ideation, thoughts, or behaviors in the psychiatric patient population. Therefore, for central-nervous-system safety, the C-SRRS test will be conducted at screening and check-in to exclude subjects with suicidal ideation and prior to discharge to ensure subjects' safety with regard to suicidal ideation behavior. If, during study conduct, a subject develops depressive symptoms, the C-SSRS test may be administered at the investigator's discretion.

The C-SSRS is a semi-structured interview that captures the occurrence, severity, and frequency of suicide-related thoughts and behaviors during the assessment period. The interview includes definitions and suggested questions to solicit the type of information needed to determine if a suicide-related thought or behavior has occurred. The interview and rating for the C-SSRS must be completed by a licensed clinician or designee who has completed the required rater training to complete this assessment and who has been approved by the sponsor to administer this assessment. Documentation of training should be maintained in the trial site's files.

The "Baseline/Screening" version of the C-SSRS will be completed at screening and the "Since Last Visit" version will be completed at all other specified visits (including ET, if applicable). The "Baseline/Screening" version be used to assess Suicidal Ideation and Suicidal Behavior in both the subjects' lifetime and within the past 12 months prior to screening. There are a maximum of 19 items to be completed: 7 required, 10 potential additional items if there is a positive response to a required item, and 2 items for suicide/suicide behavior present during the interview. The C-SSRS uses dichotomous scales (ie, yes or no), Likert scales, and text or narrative to further describe the thoughts or behaviors.

8.6 Adverse Events

8.6.1 Definitions

Trial interventions are all pre-specified, investigational and noninvestigational medicinal products, intended to be administered to the subjects during the conduct of the trial.

Adverse Event: An AE is defined as any untoward medical occurrence in a clinical trial subject administered a trial intervention and which does not necessarily have a causal relationship with this intervention. Adverse events would not include information recorded as medical history at screening for pre-planned procedures for which the underlying condition was known and no worsening occurred. An adverse reaction is any untoward and unintended response to a trial intervention related to any dose administered.

A suspected adverse reaction is any AE for which there is a reasonable possibility that the trial intervention caused the AE. For the purpose of Investigational New Drug (IND) safety reporting, “reasonable possibility” means there is evidence to suggest a causal relationship between the trial intervention and the AE. Suspected adverse reaction implies a lesser degree of certainty about causality.

Treatment-emergent AEs (TEAEs) are defined as AEs with an onset date on or after the start of IMP treatment. In more detail, TEAEs are all AEs which started after the start of IMP; or if the event was continuous from baseline and worsens either in intensity or frequency, becomes serious, is assessed as IMP-related or results in death.

A Serious Adverse Event (SAE) includes any event that results in any of the following outcomes:

- Death.
- Life-threatening; ie, the subject was, in the opinion of the investigator, at immediate risk of death from the event as it occurred. It does not include an event that, had it occurred in a more severe form, might have caused death.
- Persistent or significant incapacity/disability or substantial disruption of the ability to conduct normal life functions.
- Requires inpatient hospitalization or prolongs hospitalization.
- Hospitalization itself should not be reported as an SAE; whenever possible the reason for the hospitalization should be reported.
 - Hospitalizations or prolonged hospitalizations for social admissions (ie, those required for reasons of convenience or other nonmedical need) are not considered SAEs.
 - Prescheduled hospitalization to address a condition that has existed prior to the signing of the ICF should not be considered an SAE and should be recorded as medical history.
- Congenital anomaly/birth defect.
- Other medically significant events that, based upon appropriate medical judgment, may jeopardize the subject and may require medical or surgical intervention to prevent one of the outcomes listed above, eg, allergic bronchospasm requiring intensive treatment in an emergency room or home, blood dyscrasias or convulsions that do not result in hospitalization, or the development of drug dependency or drug abuse.

Nonserious AEs are all AEs that do not meet the criteria for a “serious” AE.

Adverse Events of Special Interest (AESIs): A noteworthy event for the particular IMP or class of products that a sponsor may wish to monitor carefully. All AESIs are to be reported as immediately reportable events (IREs). No AESIs have been identified for the IMP to be administered during this trial.

Immediately Reportable Event:

- Any SAE.
- Potential serious hepatotoxicity (see [Section 8.6.6](#)).
- Any AE related to occupational exposure (eg, an investigator getting a skin rash after exposure to a medication). Non-subject AEs would not be recorded on the eCRF form but must be recorded on an IRE form to the sponsor.
- Pregnancies are also defined as IREs. Although normal pregnancy is not an AE, pregnancy of a trial subject will mandate trial intervention discontinuation and pregnancy of either a subject or a subject's partner must be reported on an IRE form and the Pregnancy Surveillance Form(s) to the sponsor. This includes pregnancy of the subject or the partner of the subject. Pregnancy will only be documented on the AE eCRF if the pregnancy occurs in a female subject and there is an abnormality or complication (see [Section 10.3](#)).

Clinical Laboratory Test Value Changes: It is the investigator's responsibility to review the results of laboratory tests for each individual subject as they become available. This review will be documented by the investigator's dated signature on the laboratory report. The investigator may repeat the laboratory test or request additional tests to verify the results of the original laboratory tests. If this laboratory value is considered medically relevant (ie, clinically significant) by the investigator (subject is symptomatic, requiring corrective treatment or further evaluation), or if the laboratory value leads to discontinuation, and/or fulfills a seriousness criterion, this is considered an AE.

Severity: Adverse events will be graded on a 3-point scale and reported as indicated in the eCRF. The severity of an adverse experience is defined as follows:

- 1 = Mild:** Discomfort noticed, but no disruption to daily activity.
- 2 = Moderate:** Discomfort sufficient to reduce or affect normal daily activity.
- 3 = Severe:** Inability to work or perform normal daily activity.

IMP Causality: Assessment of causal relationship of an AE to the use of the IMP is defined as follows:

- Related:** There is a reasonable possibility of a temporal and causal relationship between the IMP and the AE.
- Not Related:** There is no temporal or causal relationship between the IMP and the AE.

8.6.2 Eliciting and Reporting Adverse Events

The investigator will regularly assess subjects for the occurrence of AEs. To avoid bias in eliciting AEs, subjects should be asked the nonleading question: "How have you felt since your last visit?" All AEs (serious and nonserious) reported by the subject must be

recorded on the source documents and eCRF provided by the sponsor. Adverse event collection will begin after a subject, or parent/legal guardian, signs the ICF, and will continue until the 30-day follow-up phone call. All AEs must be reported after subject informed consent/assent has been obtained, including screening failures due to AEs, irrespective of trial intervention administration.

Medical terminology should be used for AE reporting. Adverse events should be reported as a single unifying diagnosis whenever possible or, in the absence of a unifying diagnosis, as individual signs or symptoms.

Exacerbation or disease progression should be reported as an AE only if there are unusual or severe clinical features that were not present, or experienced earlier, or not expected based on the course of the condition.

Medical or surgical procedures (eg, endoscopy, appendectomy) should not be reported as AEs; however, the condition that led to the procedure may be reported as an AE.

If a reported AE undergoes a change or worsening in severity, seriousness, or toxicity, it should be reported as a new AE in the eCRF.

In addition, the sponsor must be notified immediately by telephone, fax, or e-mail of any IREs according to the procedure outlined below, in [Section 8.6.3](#). Special attention should be paid to recording hospitalization and concomitant medications.

The AE, start date, end date (if possible, start date and time, end date and time), seriousness, severity, relationship to IMP (causality), action taken with IMP, and outcome will be recorded on the source documents and in the eCRF.

Note: Start time should be recorded in the event an AE such as vomiting occurs. When capturing start/end time, at a minimum, the hour should be captured in the event it is difficult to specify in hours and minutes.

Regarding SAE, relationship to, and action taken with trial intervention(s) other than IMP will also be evaluated per each intervention. These evaluations will be recorded in the source documents and in the eCRF and will be reported using the IRE form (see [Section 8.6.3](#)).

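### Protocol 8.6.2 sets a narrower threshold for reporting an exacerbation than the TEAE definition sets for counting one, so a mild, expected worsening of a medical-history condition may go unreported

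*Protocol*

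**What the plan says.** Three parts of the plan bear on this point.

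- **Definitions (protocol 8.6.1).** An AE is "any untoward medical occurrence in a clinical trial subject administered a trial intervention", with no severity threshold. The one exclusion concerns history recorded for pre-planned procedures, and only those "for which the underlying condition was known and no worsening occurred". An event already present at baseline becomes treatment-emergent "if the event was continuous from baseline and worsens either in intensity or frequency, becomes serious, is assessed as IMP-related or results in death". SAP 10.2 carries the same worsening clause.
- **Reporting (protocol 8.6.2).** All AEs reported by the subject go on the source documents and the eCRF. Two further sentences qualify this. On exacerbations: "Exacerbation or disease progression should be reported as an AE only if there are unusual or severe clinical features that were not present", continuing "or experienced earlier, or not expected based on the course of the condition". On AEs already recorded: "If a reported AE undergoes a change or worsening in severity, seriousness, or toxicity, it should be reported as a new AE".
- **Timing (protocol 8.6.2).** "Adverse event collection will begin after a subject, or parent/legal guardian, signs the ICF", and collection runs to the 30-day follow-up call.

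Separately, protocol 8.5.1 to 8.5.4 send laboratory, examination, vital-sign and ECG abnormalities to the AE eCRF when they arise after screening and the investigator judges them clinically significant.

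**The concern.** The rule for what the site reports is narrower than the rule for what the analyst counts. Suppose a subject has a minor complaint in the medical history, and it becomes somewhat more frequent or more intense during dosing, in a way that is ordinary for that complaint. The TEAE definition includes that worsening; the exacerbation sentence tells the site not to report it.

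The sentence reads as if written for a trial in patients, where progression of the studied disease would otherwise fill the AE tables. Here the subjects are healthy, so there is no disease under study whose expected course needs to be set aside. Minor conditions can still be present: exclusion criterion 1 removes clinically significant history only, and SAP 8.3 plans a medical-history listing.

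Safety and tolerability is the secondary objective. SAP 10.2 tabulates TEAEs overall, by severity and by relationship to each drug, and every one of those tables depends on what the site enters. SAP 6.8 imputes no missing safety data, and an event never entered could not be recovered in any case.

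**Working it through.** The plan gives no figure on this point, so the check is a comparison of texts, followed by one line of arithmetic.

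**Step 1: Which worsenings reach the AE record?** Inputs are protocol 8.5.1 to 8.5.4, 8.6.1 and 8.6.2, and SAP 10.2.

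| Case | Meets the TEAE definition? | Reported under the protocol? |
|---|---|---|
| (a) Event starting between consent and first dose, then worse in severity | Yes | Yes, as a new AE |
| (b) Same event, worse in frequency only | Yes | Unclear: the new-AE sentence names severity, seriousness and toxicity, not frequency |
| (c) Medical-history condition, worse with new unusual or severe features | Yes | Yes |
| (d) Medical-history condition, worse mildly and as expected | Yes | No: the exacerbation sentence excludes it |
| (e) Clinically significant laboratory, examination, vital-sign or ECG worsening | Yes | Yes, under 8.5.1 to 8.5.4 |

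Case (d) is the conflict. Case (b) is a smaller gap of the same kind.

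**Step 2: Does the ambiguity in the exacerbation sentence matter?** Its last clause can be read in two ways. If being unexpected is a separate ground for reporting, a mild but unexpected worsening is reported. If it only qualifies the unusual or severe features, a mild unexpected worsening is lost too. Case (d) is both mild and expected, so it goes unreported on either reading.

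**Step 3: Does another route pick up case (d)?**
- The all-AEs rule is general. The exacerbation sentence in the same section is a specific exception, and a site following the protocol would apply it.
- The new-AE sentence starts from a reported AE. A condition held only as medical history is not one.
- The rules in 8.5.1 to 8.5.4 need a finding judged clinically significant. A mild symptom does not qualify.
- The clause that makes an event treatment-emergent when it is assessed as IMP-related does not help, because under 8.6.2 relationship is entered for an AE that has been recorded.

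**Step 4: Size per missed subject.** With 12 dosed subjects in a part (protocol 9.1), a subject counts towards overall TEAE incidence once, however many events occur. Incidence falls only if the missed worsening was that subject's sole TEAE. The fall is then 1/12 = 0.083, or 8.3 percentage points. The documents do not say how many such subjects to expect, and the number may be zero.

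**The case against.** The strongest reply is that the sentence is nearly inert here. Subjects must be in good health, clinically significant history is excluded with neurologic, respiratory and immunologic disease named as examples, and most medication is barred in the 14 days before dosing. Few conditions are left to worsen, and many complaints that arise during dosing, such as a fresh headache, would naturally be entered as new AEs. The safety summaries are descriptive, and the same reporting rule applies in both periods of each part. All of this stands, and it is why the effect is probably small. It does not remove the conflict, because minor history remains possible.

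A second reply is that the TEAE definition applies only to AEs, so a worsening excluded by 8.6.2 is not an AE and there is nothing to reconcile. This does not succeed. Section 8.6.1 defines an AE without a threshold, and its one exclusion requires that no worsening occurred. Section 8.6.2 governs reporting; it does not redefine the term.

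Two stronger readings are tempting, and the documents support neither.
- A reader might infer that ordinary worsenings are never recorded. Cases (a), (c) and (e) show that several kinds are captured. Protocol 10.1.7.2 also requires source notes on general subject status, so an event not reported as an AE may still be noted elsewhere.
- A reader might assume, say, three affected subjects per part and conclude that incidence is understated by 3/12 = 25 points. The arithmetic is right, but the count is invented. The documents give no frequency of minor pre-existing conditions, and zero is as consistent with them as three. They show that under-counting is possible, not that it will occur.

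**Conclusion.** The inconsistency is real and limited. Protocol 8.6.2 reports an exacerbation on narrower grounds than protocol 8.6.1 and SAP 10.2 use to count one. The event at risk is a mild, expected worsening of a condition held only as medical history. A frequency-only worsening of an already reported AE is also left unclear.

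Any bias in TEAE incidence would be downward, in steps of 8.3 percentage points per affected subject. That step assumes 12 dosed subjects in the part and that the missed event is the subject's only TEAE. The total cannot be derived from the documents and is probably small. The primary PK endpoints do not depend on it. The sentence should still be changed: it is a stated instruction that conflicts with the definition used in the analysis, and the correction is nearly free.

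**What to change.** Make two changes in protocol 8.6.2:

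1. Replace the exacerbation and disease-progression sentence with: *Any worsening in intensity or frequency of a condition present before the first dose is reported as an AE.*
2. Add *frequency* to the sentence that makes a changed or worsened reported AE a new AE.

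Reporting then matches protocol 8.6.1 and SAP 10.2, and the TEAE definitions need no edit. The cost is two small wording changes, a line in site training and a few more mild AE records. The change has to be in place before data are collected, because the analysis cannot restore events that the site was told not to report.

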8.6.3 Immediately Reportable Events

The investigator must immediately report (within 24 hours), using an IRE form, after he/she or site personnel become aware of any IRE (SAE, AE related to occupational exposure, potential serious hepatotoxicity, or confirmed pregnancy), by telephone, fax, or e-mail to the sponsor or designee using the contact information on the cover page of this protocol (please note that the IRE form is NOT the AE eCRF). Patient confidentiality

must be protected and contact information such as name, address, phone number or any other protected health information as determined by applicable local regulation must be redacted when forwarding safety information and supporting documentation. Details regarding the follow-up of IREs are included in [Section 8.6.8.2](#).

8.6.4 Medical Device Incidents (Including Malfunctions)

Not applicable.

8.6.5 Adverse Events of Special Interest

Not applicable.

8.6.6 Potential Serious Hepatotoxicity

For a subject who experiences an elevation in AST or ALT that is ≥ 3 times the upper limit of normal (ULN), a total bilirubin level should also be evaluated. If the total bilirubin is ≥ 2 times the ULN, complete an IRE form with all values listed and report as an AE in the eCRF. Details regarding the follow-up of IREs are included in [Section 8.6.8.2](#).

8.6.7 Procedure for Breaking the Blind

This trial does not use blinding procedures.

8.6.8 Follow-up of Adverse Events

8.6.8.1 Follow-up of Nonserious Adverse Events

Nonserious AEs that are identified at any time during the trial must be recorded on the AE eCRF with the current status (ongoing or resolved/recovered) noted. All nonserious events (that are not IREs) that are ongoing at the last scheduled contact will be recorded as ongoing in the eCRF. For any AE having been identified throughout the trial, or during analysis, additional relevant medical history information may be requested by the sponsor to further ascertain causality (including, but not limited to, information such as risk-related behavior, family history, and occupation).

8.6.8.2 Follow-up of Immediately Reportable Events

This trial requires that subjects be actively monitored for IREs up to 30 days after the last dose of IMP is administered.

Immediately reportable events that are **identified or ongoing at the last scheduled contact** must be recorded as such on the AE eCRF page and the IRE form. If updated information (eg, resolved status) on IRE status becomes available after a subject's last scheduled contact (up to last in-clinic visit for the entire trial), this must be reported to the

sponsor and recorded on the AE eCRF page and the IRE form, according to the appropriate reporting procedures described in [Section 8.6.3](#).

It is expected that the investigator will provide or arrange appropriate supportive care for the subject and will provide prompt updates on the subject's status to the sponsor. The investigator will follow the IREs until:

- the events are resolved,
- the events have stabilized,
- the subject is lost to follow-up, or
- the subject has died.

Resolution means that the subject has returned to the baseline state of health and stabilized means that the investigator does not expect any further improvement or worsening of the subject's condition. The investigator will continue to report any significant follow-up information to the sponsor up to the point the event has resolved or stabilized, or the subject is lost to follow-up, or has died.

Refer to [Section 10.3](#) for additional information regarding the follow-up period for subjects that become pregnant or for pregnant partners of male subjects.

8.6.8.3 Follow-up and Reporting of Immediately Reportable Events Occurring After Last Scheduled Contact

Any new IREs reported to the investigator which occur after the last scheduled contact and are determined by the investigator to be reasonably associated with the use of the trial intervention(s), should be reported to the sponsor according to the procedures outlined in [Section 8.6.3](#). This may include IREs that are captured on follow-up telephone contact or at any other time point after the defined trial period. Any significant follow-up information should continue to be reported to the sponsor until the events are resolved or stabilized, or the subject is lost to follow-up or has died.

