An analysis of variance will be performed on the log-transformed PK parameters C_{\max} , AUC_t , and AUC_{∞} for OPC-167832 and/or its metabolites using the MIXED procedure in SAS for each part separately. The mixed-effects linear model for each PK parameter will include treatment (OPC-167832 + potentially interacting drug [test] and OPC-167832 alone [reference]) as a fixed effect and subject as a random effect. From each analysis, mean differences between the treatments OPC-167832 + potentially interacting drug and OPC-167832 alone and the 90% CI for the differences will be derived. The antilog of the differences will then provide an estimate of the geometric mean ratios (GMR; OPC-167832 + potentially interacting drug/OPC-167832 alone), and the antilog of the confidence limits will provide the 90% CIs for the GMRs.

Trial Duration: Each subject in this trial is expected to participate in the following periods of the trial (approximate durations listed):

- Eligibility screening period: Day –28 to Day –2
- In-clinic treatment (2 dosing periods):
 - Part 1: Day –1 to Day 26 days (27 days)
 - OR
 - Part 2: Day –1 to Day 32 (33 days)
- Safety follow-up phone call: 30 (+ 2) days after the last dose of OPC-167832 (eg, Day 45 [+ 2 days] for Part 1 and Day 55 [+ 2 days] for Part 2 for trial completers).

The trial start is defined as the date the first subject signs their informed consent form. Overall, the trial duration, from signing of the first subject's informed consent form to the last subject's final assessment, is expected to be approximately 11 weeks for Part 1 and approximately 12 weeks for Part 2.

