4.1 Type/Design of Trial

This is a single-center, 2-part, open-label DDI trial in healthy adult subjects. Part 1 and Part 2 will have fixed sequence designs with 12 subjects in each part for a total of 24 subjects enrolled.

- Part 1: OPC-167832 + itraconazole (strong CYP3A inhibitor)
- Part 2: OPC-167832 + carbamazepine (strong CYP3A inducer)

Following a screening period of up to 28 days, eligible subjects will enter the clinic on the day prior to the first treatment day (Day -1).

For Part 1, the impact of CYP3A inhibition on the PK of OPC-167832 will be assessed. Subjects will receive a single, 30-mg, oral dose of OPC-167832 **CCI** in the fasted state on Day 1 with blood collections for PK assessment of OPC-167832 from Day 1 through Day 8. On Day 8, subjects will receive 200-mg doses of itraconazole in the morning and evening (200 mg twice daily [BID]) followed by 200 mg of itraconazole administered QD on Day 9 through Day 14 to approach steady-state conditions for itraconazole. On Day 15, a single, 30-mg, oral dose of OPC-167832 **CCI** will

be administered concurrently with a 200-mg dose of itraconazole in the fasted state with blood collections for PK assessment of OPC-167832 from Day 15 through Day 26. Once daily 200-mg doses of itraconazole will continue to be administered on Day 16 through Day 25. Subjects will be discharged from the clinic after the PK sample on Day 26 or early termination (ET).

For Part 2, the impact of CYP3A induction on the PK of OPC-167832 will be assessed. Subjects will receive a single, 30-mg, oral dose of OPC-167832 CCI on Day 1 in the fasted state with blood collections for PK assessment of OPC-167832 from Day 1 through Day 8. On Day 8 through Day 10, subjects will receive 100 mg BID carbamazepine followed by 200 mg BID carbamazepine administration on Day 11 through Day 13 and 300 mg BID carbamazepine administration on Day 14 through Day 31. On Day 25, a 30-mg oral dose of OPC-167832 CCI will be administered concurrently with the morning 300 mg dose of carbamazepine in the fasted state with blood collections for PK assessment of OPC-167832 from Day 25 through Day 32. Subjects will be discharged from the clinic after the PK sample on Day 32 or ET.

All subjects will be contacted by phone 30 days after the last dose of OPC-167832 to assess any new or ongoing AEs and to record concomitant medications.

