6.4 Safety Analysis Set

The safety dataset will include all enrolled subjects who have taken at least one dose of IMP.

In Part 1 of this trial, Investigational Medicinal Product (IMP) refers to OPC-167832 and/or itraconazole, and in Part 2 of this trial, IMP refers to OPC-167832 and/or carbamazepine.

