10.2 Adverse Events

All AEs will be coded by Medical Dictionary for Regulatory Activities (MedDRA, Version 25 or a later version if available).

Treatment-emergent adverse events (TEAEs) are defined as AEs with an onset date on or after the start of IMP treatment. TEAEs are all AEs which started after the start of IMP treatment; or if the event was continuous from baseline and worsens either in intensity or frequency, becomes serious, is assessed as IMP-related or results in death.

Relatedness of AEs to IMP will be collected for each IMP, individually, OPC 167832 and itraconazole for Part 1 and OPC 167832 and carbamazepine for Part 2.

A Serious Adverse Event (SAE) includes any event that results in any of the following outcomes:

- Death.
- Life-threatening; ie, the subject was, in the opinion of the investigator, at immediate risk of death from the event as it occurred. It does not include an event that, had it occurred in a more severe form, might have caused death.
- Persistent or significant incapacity/disability or substantial disruption of the ability to conduct normal life functions.
- Requires inpatient hospitalization or prolongs hospitalization.
Hospitalization itself should not be reported as an SAE; whenever possible the reason for the hospitalization should be reported.
 - Hospitalizations or prolonged hospitalizations for social admissions (ie, those required for reasons of convenience or other nonmedical need) are not considered SAEs.
 - Prescheduled hospitalization to address a condition that has existed prior to the signing of the ICF should not be considered an SAE and should be recorded as medical history.
- Congenital anomaly/birth defect.

Quabodepistat (OPC-167832)

Study 323-201-00007

- Other medically significant events that, based upon appropriate medical judgment, may jeopardize the subject and may require medical or surgical intervention to prevent one of the outcomes listed above, eg, allergic bronchospasm requiring intensive treatment in an emergency room or home, blood dyscrasias or convulsions that do not result in hospitalization, or the development of drug dependency or drug abuse.

Nonserious AEs are all AEs that do not meet the criteria for a “serious” AE.

The frequency and percentage of subjects with the following events, together with the number of events, (events listed below), will be summarized by SOC, MedDRA preferred term, severity, and treatment for each of Part 1 and Part 2 separately

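### The follow-up call is timed from the last OPC-167832 dose, so completers are called only 20-22 days after itraconazole or 24-26 days after carbamazepine; if those drugs are IMP, the 30-day monitoring window is cut 8-10 or 4-6 days short

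*Protocol*

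**What the plan says.** Protocol Section 8.6.8.2 sets the monitoring period for IREs: "This trial requires that subjects be actively monitored for IREs up to 30 days after the last dose of IMP is administered".

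The Trial Duration part of the Protocol synopsis times the last contact differently: "Safety follow-up phone call: 30 (+ 2) days after the last dose of OPC-167832". For completers it gives Day 45 (+2) in Part 1 and Day 55 (+2) in Part 2. Section 4.1, both schedules of assessments (Tables 1.3-1 and 1.3-2) and SAP Section 3.1 use the same anchor. Under Section 8.6.2, adverse-event collection "will continue until the 30-day follow-up phone call".

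The partner drugs outlast OPC-167832. Section 4.1 says for Part 1: "Once daily 200-mg doses of itraconazole will continue to be administered on Day 16 through Day 25". For Part 2 it specifies "300 mg BID carbamazepine administration on Day 14 through Day 31". The last OPC-167832 doses are on Day 15 and Day 25.

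Whether the partner drugs are IMP depends on where one looks. SAP Section 6.4 is explicit: in Part 1 "Investigational Medicinal Product (IMP) refers to OPC-167832 and/or itraconazole", and in Part 2 "IMP refers to OPC-167832 and/or carbamazepine". SAP Section 10.2 agrees: "Relatedness of AEs to IMP will be collected for each IMP, individually". The Protocol has no single definition and points both ways.

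**The concern.** The requirement runs from one event and the contact meant to satisfy it runs from another. If IMP includes itraconazole and carbamazepine, the last scheduled contact and the end of adverse-event collection both come before the 30 days are up. A site cannot tell from the text on which day its active-monitoring duty ends.

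What is at stake is a new serious event arising late after the last partner-drug dose. No scheduled contact would elicit it. After the call, Section 8.6.8.3 covers only new IREs that reach the investigator and are judged reasonably associated with a trial intervention. Safety of the combinations is the trial's secondary objective, and the Protocol itself names myelosuppression (Table 1.3-2, footnote b) and suicidal ideation (Section 8.5.5) as carbamazepine risks.

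**Working it through.** **Inputs.** Last OPC-167832 dose: Day 15 (Part 1), Day 25 (Part 2), from Table 6.1-1. Last partner-drug dose: itraconazole Day 25, carbamazepine Day 31, same table. Call: 30 to 32 days after the last OPC-167832 dose (synopsis). Required window: 30 days after the last IMP dose (Section 8.6.8.2).

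**The plan's own figure.** Call day = last OPC-167832 day + 30. Part 1: 15 + 30 = Day 45. Part 2: 25 + 30 = Day 55. Both match the synopsis; with the +2 allowance the calls fall on Day 45-47 and Day 55-57.

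**Completers.** Follow-up = call day − last partner-drug day. Gap = (last partner-drug day + 30) − call day.

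| | Part 1 (itraconazole) | Part 2 (carbamazepine) |
|---|---|---|
| Follow-up after partner drug | 45 − 25 = 20 to 47 − 25 = 22 days | 55 − 31 = 24 to 57 − 31 = 26 days |
| Window end if partner drug is IMP | 25 + 30 = Day 55 | 31 + 30 = Day 61 |
| Gap if partner drug is IMP | 55 − 47 = 8 to 55 − 45 = 10 days | 61 − 57 = 4 to 61 − 55 = 6 days |
| Gap if IMP is OPC-167832 only | 0 days | 0 days |

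These are calendar days. The last carbamazepine dose is in the evening, so elapsed time in Part 2 may be about half a day less.

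**Subjects who start the partner drug but stop before the second OPC-167832 dose.** Section 7.3 asks them to complete follow-up if at all possible. Their last OPC-167832 dose is Day 1, so the call is Day 31-33.

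| Last partner-drug dose | Follow-up | Window end (wide reading) | Gap (wide reading) |
|---|---|---|---|
| Itraconazole, Day 8 | 23-25 days | Day 38 | 5-7 days |
| Itraconazole, Day 14 | 17-19 days | Day 44 | 11-13 days |
| Carbamazepine, Day 8 | 23-25 days | Day 38 | 5-7 days |
| Carbamazepine, Day 24 | 7-9 days | Day 54 | 21-23 days |

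The documents do not give dropout timing. With 12 enrolled for about 10 completers, I assume 0-2 such subjects per part.

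**Which reading of IMP?**

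- *Wide (partner drugs included).* Besides SAP 6.4 and 10.2, both schedules list the partner drugs under the IMP administration heading. They also schedule compliance checks on days with a partner drug only, citing Protocol Section 6.4, which covers IMP doses. Exclusion criteria 20 and 21 count the 90-day contraception and sperm-donation limits from the last IMP dose, while Section 10.3 counts the same limits from the last trial intervention, as if the terms were interchangeable.
- *Narrow (OPC-167832 only).* The synopsis names only OPC-167832 as the investigational product. The abbreviation list includes NIMP. Sections 6.1 and 8.6.1 distinguish investigational from noninvestigational products, Section 8.6.2 refers to interventions that are not IMP, and under Section 6.2.1 the site buys the partner drugs.

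The Protocol does not settle the question.

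**The case against.** The strongest reply is that the OPC-167832 anchor is deliberate. It recurs in the synopsis, Section 4.1, both schedules and SAP 3.1, and the duration line fits it: 28 screening days plus 45-47 days is 73-75 days, about 11 weeks; 28 plus 55-57 is 83-85 days, about 12 weeks. A specific anchor used so often is a fair guide to what the general word IMP meant in 8.6.8.2, and on that reading nothing required is missed. The SAP definition places no obligation on a site. On the wide reading, 8.6.8.2 itself obliges monitoring to 30 days whatever the call schedule. Nothing in the documents shows that 20-26 days is too short for these two drugs.

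There are safeguards as well. Completers have an examination, vital signs, ECG and laboratory tests at discharge, the day after the last partner-drug dose, and Part 2 allows optional further observation. Section 7.3 calls for every effort to follow an event that led to stopping treatment until it resolves or stabilises. Section 10.3 requires pregnancies to be reported for at least 90 days after the last trial intervention. A phone call cannot detect laboratory-defined hepatotoxicity. The 7-9 day case needs a subject to take carbamazepine through Day 24 and then stop.

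Most of this stands as a limit on weight, and a schedule breach is not shown. It does not remove the conflict. If 8.6.8.2 obliges monitoring to Day 55 or Day 61, a schedule whose last contact and end of adverse-event collection come earlier does not provide for it. The discharge tests say nothing about later events, and following the event that caused a withdrawal does not elicit a new one.

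**Conclusion.** The concern holds, as a design point worth correcting and not as a proven violation. On either reading, completers have 20-22 days of follow-up after itraconazole and 24-26 days after carbamazepine. Measured against 8.6.8.2, the shortfall is 8-10 of 30 days in Part 1 and 4-6 of 30 days in Part 2 if the partner drugs are IMP, and zero if they are not. For the few subjects who might stop between starting the partner drug and the second OPC-167832 dose, follow-up is 17-25 days (Part 1) or 7-25 days (Part 2), with a wide-reading gap of 5-13 or 5-23 days.

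The completer day counts rest on the stated schedule alone. The shortfall depends on which definition of IMP governs, and the number of early stoppers is an assumption. The effect is confined to safety follow-up; the PK endpoints are untouched.

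**What to change.** Adopt one definition of IMP in the Protocol and the SAP. Time the follow-up call and the end of adverse-event collection at 30 (+2) days after the last dose of any trial drug, for early terminators too. For completers that is 25 + 30 = Day 55 (+2) in Part 1 and 31 + 30 = Day 61 (+2) in Part 2. Change the synopsis, Section 4.1, both schedules and SAP 3.1, and have the sponsor re-estimate the trial-duration line.

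The cost is a call 10 days later in Part 1 and 6 days later in Part 2. For subjects who stop before the second OPC-167832 dose it is at most 44 − 31 = 13 or 54 − 31 = 23 days later. Participation is slightly longer, with a little more risk of loss to follow-up. The change needs a protocol amendment under Section 10.4, but no extra visit, blood sample or procedure.

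If the sponsor prefers to keep the present call, the minimum is a sentence in 8.6.8.2 stating that the 30 days run from the last OPC-167832 dose. That removes the ambiguity but leaves the shorter follow-up after the partner drugs as it is.
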